13.1 Regulatory and ethical compliance

This clinical study was designed and shall be implemented, executed and reported in accordance with the ICH Harmonized Tripartite Guidelines for Good Clinical Practice, with applicable local regulations (including European Directive 2001/20/EC, US CFR 21), and with the ethical principles laid down in the Declaration of Helsinki.

13.2 Responsibilities of the investigator and IRB/IEC

Before initiating a trial, the investigator/institution must obtain approval/favorable opinion from the Institutional Review Board/Independent Ethics Committee (IRB/IEC) for the trial protocol, written informed consent form, consent form updates, participant recruitment procedures (e.g., advertisements) and any other written information to be provided to participants. Prior to study start, the investigator is required to sign a protocol signature page confirming his/her agreement to conduct the study in accordance with these documents and all of the instructions and procedures found in this protocol and to give access to all relevant data and records to Novartis monitors, auditors, Novartis Quality Assurance representatives, designated agents of Novartis, IRBs/IECs, and regulatory authorities as required. If an inspection of the clinical site is requested by a regulatory authority, the investigator must inform Novartis immediately that this request has been made.

13.3 Publication of study protocol and results

The protocol will be registered in a publicly accessible database such as clinicaltrials.gov and as required in EudraCT. In addition, after study completion (defined as last patient last visit) and finalization of the study report the results of this trial will be submitted for publication and posted in a publicly accessible database of clinical trial results, such as the Novartis clinical trial results website and all required Health Authority websites (e.g., Clinicaltrials.gov, EudraCT etc.).

For details on the Novartis publication policy including authorship criteria, please refer to the Novartis publication policy training materials that were provided at the trial investigator meetings.

13.4 Quality Control and Quality Assurance

Novartis maintains a robust Quality Management System (QMS) that includes all activities involved in quality assurance and quality control, to ensure compliance with written Standard Operating Procedures as well as applicable global/local GCP regulations and ICH Guidelines.

Audits of investigator sites, vendors, and Novartis systems are performed by auditors, independent from those involved in conducting, monitoring or performing quality control of the clinical trial. The clinical audit process uses a knowledge/risk based approach.

Audits are conducted to assess GCP compliance with global and local regulatory requirements, protocols and internal SOPs, and are performed according to written Novartis processes.

13.5 Participant Engagement

The following participant engagement initiatives are included in this study and will be provided, as available, for distribution to study participants at the timepoints indicated. If compliance is impacted by cultural norms or local laws and regulations, sites may discuss modifications to these requirements with Novartis.

- Thank You letter
- Plain language trial summary - after CSR publication
- Individual study results - after CSR publication
- Trial Feedback Questionnaires (TFQ) - 3 timepoints: at the start, during and at the end of the trial.

[figure not shown]
14 Protocol adherence

This protocol defines the study objectives, the study procedures and the data to be collected on study participants. Additional assessments required to ensure safety of participants should be administered as deemed necessary on a case by case basis. Under no circumstances including incidental collection is an investigator allowed to collect additional data or conduct any additional procedures for any purpose involving any investigational drugs under the protocol, other than the purpose of the study. If despite this interdiction prohibition, data, information, observation would be incidentally collected, the investigator shall immediately disclose it to Novartis and not use it for any purpose other than the study, except for the appropriate monitoring on study participants.

Investigators ascertain they will apply due diligence to avoid protocol deviations. If an investigator feels a protocol deviation would improve the conduct of the study this must be considered a protocol amendment, and unless such an amendment is agreed upon by Novartis and approved by the IRB/IEC and Health Authorities, where required, it cannot be implemented.

[figure not shown]

16.1 Appendix 1: Clinically notable laboratory values and vital signs

The following specific criteria have been identified for this study. Should these criteria be met, a re-test must be done within 5 days after the first assessment. Discontinuation of the study treatment should be considered if the abnormal hematology parameter is confirmed:

- Hemoglobin: < 10 g/dl
- Platelets: < 75 000/mm³
- Leukocytes: < 3 000/mm³
- Neutrophils: < 1 500/mm³

For all other laboratory assessments, the central laboratory will flag laboratory values falling outside of the normal ranges on the central laboratory report (which the investigator should review and sign-off) and the investigator will report any values considered clinically significant in the eCRF.

Refer to [Section 16.2](#) for clinically notable laboratory values for hepatotoxicity.

Refer to [Section 16.3](#) for clinically notable laboratory values for nephrotoxicity.

Notable values for vital signs and change from baseline will be summarized.

Notable values are defined as follows:

- heart rate of < 50 or > 100 bpm
- systolic blood pressure of < 90 and \geq 140 mmHg
- diastolic blood pressure of < 60 and \geq 90 mmHg

For ECGs, a notable QTc value is defined as an absolute QTc (Fridericia's) interval of greater than 450 msec for males or greater than 460 msec for females or QTcF increase of \geq 60 msec compared to baseline QTcF value – all such ECGs will be flagged by the central CRO's cardiologist and require assessment for clinical relevance by the investigator.

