14. Evidence of clinically significant cardiovascular (such as but not limited to myocardial infarction, unstable ischemic heart disease, NYHA Class III/IV left ventricular failure, arrhythmia and uncontrolled hypertension within 12 months prior to Visit 1), neurological, psychiatric, pulmonary, renal, hepatic, endocrine, metabolic, hematological disorders, gastrointestinal disease or immunodeficiency that, in the investigator's opinion, would

- compromise the safety of the participant, interfere with the interpretation of the study results or otherwise preclude participation or protocol adherence of the participant
15. Uncontrolled disease states, such as asthma, or inflammatory bowel disease, where flares are commonly treated with oral or parenteral corticosteroids
 16. Hematology parameters at screening:
 - Hemoglobin: < 10 g/dl
 - Platelets: < 100 000/mm³
 - Leucocytes: < 3 000/mm³
 - Neutrophils: < 1 500/mm³
 17. Significant bleeding risk or coagulation disorders
 - 18.a History of gastrointestinal bleeding, e.g., in association with use of nonsteroidal anti-inflammatory drugs (NSAID), that was clinically relevant (e.g., where intervention was indicated or requiring hospitalization or blood transfusion)
 - 19.a Requirement for anti-platelet medication, except for acetylsalicylic acid up to 100 mg/d or clopidogrel up to 75 mg/d. The use of dual anti-platelet therapy (e.g., acetylsalicylic acid + clopidogrel) is prohibited.
 20. Requirement for anticoagulant medication (for example, warfarin or Novel Oral Anti-Coagulants (NOAC))
 21. History or current hepatic disease including but not limited to acute or chronic hepatitis, cirrhosis or hepatic failure or Aspartate Aminotransferase (AST)/ Alanine Aminotransferase (ALT) levels of more than 1.5 x upper limit of normal (ULN) or International Normalized Ratio (INR) of more than 1.5 at screening
 22. History of renal disease, creatinine level above 1.5x ULN, or estimated Glomerular Filtration Rate (eGFR) < 45ml/min (using the Cockcroft-Gault equation) at screening

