9.1.1 Discontinuation from study treatment

Discontinuation of study treatment for a participant occurs when study treatment is permanently stopped for any reason (prior to the protocol planned completion of study drug administration) and can be initiated by either the participant or the investigator.

The investigator must discontinue study treatment for a given participant if, he/she believes that continuation would negatively impact the participant's well-being.

Discontinuation from study treatment is required under the following circumstances:

- Participant decision (requested in writing or verbally)

- Pregnancy
- Use of prohibited treatment requiring study treatment discontinuation as detailed in [Table 6-3](#) or discontinuation of highly effective methods of contraception as detailed in [Section 5.2](#)
- Any situation in which continued study participation might result in a safety risk to the participant
- Following emergency unblinding
- Emergence of the following AEs:
 - any adverse events that in the judgement of investigator, taking into consideration the participant's overall status, prevents the participant from continuing participation in the study, including:
 - hypersensitivity reactions,
 - severe/serious infections,
 - clinically significant spontaneous bleeding events
 - new confirmed diagnosis of malignancy of any organ system
(other than localized basal cell carcinoma of the skin or in situ cervical cancer)
 - Platelets < 75 000/mm³
 - Abnormal renal laboratory results requiring discontinuation (see [Section 16.3](#))
 - Abnormal liver laboratory results requiring discontinuation (see [Section 16.2](#))
 - Any other laboratory abnormalities that in the judgment of the investigator, taking into consideration the participant's overall status, prevents the participant from continuing participation in the study
 - participant received a live virus vaccination during the study

[figure not shown]
If discontinuation from study treatment occurs, the investigator should make a reasonable effort to understand the primary reason for the participant's discontinuation from study treatment and record this information.

All participants who discontinue from study treatment prematurely should complete the Early treatment discontinuation visit at the time of treatment discontinuation.

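### At platelets below 75 000/mm³, Protocol 9.1.1 requires study treatment to stop, Appendix 16.1 only asks that stopping be considered after a re-test, and neither text is given precedence

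*Protocol*

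**What the plan says.** Protocol 9.1.1 introduces its list with "Discontinuation from study treatment is required under the following circumstances". Among the adverse-event and laboratory items is "Platelets < 75 000/mm³", which has no re-test or judgement condition of its own. The neighbouring renal and liver items point to their appendices; the renal one begins "Abnormal renal laboratory results requiring discontinuation" and refers to 16.3. A later, separate item covers other laboratory findings and is left to discretion: "Any other laboratory abnormalities that in the judgment of the investigator". The platelet item has no pointer to 16.1.

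Appendix 16.1 lists four haematology limits, including "Platelets: < 75 000/mm³". For all four together it calls for a re-test within 5 days of the first assessment, followed by one shared sentence on action: "Discontinuation of the study treatment should be considered if the abnormal hematology parameter is confirmed".

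**The concern.** A stopping rule should give one answer for one laboratory result. Here the cut-off is identical in both places, but the instructions differ in two ways: in force (required against considered) and in trigger (any value against a confirmed value). Two sites with the same result could act differently, and each could cite the protocol.

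The item matters because cytopenia is discussed as a potential risk in Protocol 4.5 and is one of the three selected adverse events of special interest in SAP 2.7.1.1. After week 24, scheduled haematology falls only at weeks 32, 40 and 52 (Table 8-1), so a participant kept on drug could wait 8 to 12 weeks for the next scheduled count unless the investigator arranges one sooner.

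**Working it through.** No power or alpha figure is involved. The check is a comparison of the two texts, followed by a rough size.

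**1. Each situation under each text**

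| Situation | Protocol 9.1.1 | Appendix 16.1 |
|---|---|---|
| First value below the limit, re-test pending | Discontinuation required | Re-test within 5 days; silent on dosing meanwhile |
| Re-test confirms | Discontinuation required | Discontinuation to be considered |
| Re-test does not confirm | Discontinuation still required as worded | No further action stated |

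The texts differ in all three rows. In the second row they are compatible only if the site chooses to stop.

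**2. Is there reconciling text?** None was found.
- Protocol 8.4.1 cites 16.1 for the definition of notable findings, and 10.1.1 cites it for alert ranges. Neither ranks it against 9.1.1.
- Protocol 6.6 (interruptions) does not mention platelets.
- SAP 2.7.3 and Table 2-15 grade platelet counts for reporting and set no stopping rule.

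**3. Could the softer wording simply mean required?** Table 16-2 argues against that. It orders immediate discontinuation for bilirubin above 10 x ULN, but only consideration of interruption or discontinuation for liver-type symptoms. The protocol uses the two strengths for different actions.

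**4. Is the conflict confined to platelets?** Yes. Haemoglobin, leukocytes and neutrophils appear in 16.1 but are not named in 9.1.1.

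**5. Size.** The documents report no count of participants below the limit.
- The screening limit in 5.2 item 16 is "Platelets: < 100 000/mm³". From the lowest eligible count, a participant must fall by more than 100 000 - 75 000 = 25 000/mm³, which is over 25%.
- Phase 2b denominators, inferred from the bleeding percentages in Protocol 4.5: 18/267 = 6.7% on remibrutinib and 1/42 = 2.4% on placebo; 267 + 42 = 309, the stated total.
- Assumption: 0 of 267 fell below the limit over 12 weeks. One-sided 95% upper bound: 1 - 0.05^(1/267) = 1.1%.
- Applied to this trial: 0.01116 × 300 = 3.3 active-arm participants, or 0.01116 × 270 = 3.0 after the 10% drop-out assumed in 12.8.1. The range is 0 to about 3 by week 12.

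This is only an illustration. Section 4.5 calls the Phase 2b cytopenias mild and reports no notable platelet-count abnormality, but severity in this protocol (10.1.1) describes interference with activities, so zero is not established. The 267 pool six dose regimens, and the bound covers neither placebo participants nor the period after week 12.

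**The case against.** The strongest reply is that the texts can be reconciled. Section 9.1.1 is the operative discontinuation section, is mandatory and names platelets. Appendix 16.1 is a list of notable values with one general sentence for four parameters. On ordinary reading the specific rule controls, and nothing in 16.1 exempts a site from 9.1.1. This largely stands: it is the more natural reading, and it limits the practical harm. It does not remove the point, because the protocol nowhere says so.

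Second, list indentation is lost in the text available for review. If the platelet line were an example under the preceding investigator-judgement item, both texts would be discretionary. That is unlikely: the renal and liver items that follow stand alone, and the item on other laboratory abnormalities carries its own judgement clause, which would be redundant if platelets were already discretionary.

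Third, there are real safeguards:
- haematology at every scheduled visit and at unscheduled visits (Table 8-1);
- interruption for a significant safety risk (6.6);
- the duty in 9.1.1 to stop treatment that would harm the participant's well-being, and its general clause: "Any situation in which continued study participation might result in a safety risk to the participant";
- independent DMC review (10.3.1).

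These reduce the consequence. Apart from the visit schedule and the DMC, they rest on investigator judgement, and none settles which text applies at the threshold.

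A reader might infer that the protocol permits dosing to continue after a confirmed low count. The documents do not support that: a site that continued would still breach 9.1.1. A reader might also infer a platelet-count signal from 4.5. The preclinical effects described there concern platelet function and bleeding, not counts.

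**Conclusion.** The inconsistency is real and minor. At one threshold the protocol gives a mandatory stop in one place and an optional, confirmation-dependent stop in another, without ranking them. Section 9.1.1 most naturally governs, and a site that re-tests and then stops meets both. The exposure is a site that relies on 16.1 alone.

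Few participants are likely to be affected; the range of 0 to about 3 in the active arm by week 12 depends wholly on the assumed 0 of 267. The conclusion also rests on reading the platelet line in 9.1.1 as a stand-alone item.

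It would be wrong to infer a threat to the efficacy result. Under Protocol 12.4.3 and SAP 2.5.1.3, discontinuation before week 12 is handled by treatment policy, so a handful of participants stopping or continuing leaves the primary analysis essentially unchanged.

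**What to change.** State one trigger and one action in both sections.
- In 16.1, keep the shared sentence for haemoglobin, leukocytes and neutrophils, take platelets out of it, and add, for example: *Platelets < 75 000/mm³: hold study treatment and re-test within 5 days; if confirmed, discontinuation is required (see Section 9.1.1).*
- In 9.1.1, change the item to: *Confirmed platelets < 75 000/mm³ (see Section 16.1).*
- If the sponsor's medical team wants the stop at the first value, both sections should say that instead. Adding a cross-reference alone would leave the first-value or confirmed-value question open.
- If a hold is adopted, say when dosing resumes after a normal re-test. Section 6.6 otherwise places the restart after a safety interruption at the next scheduled visit, which after week 24 can be many weeks away.

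The cost is a short written amendment with the approvals listed in Protocol 14.1, which can be bundled with another amendment. Sample size and analysis do not change. The latest SAP amendment is dated 24-Jan-2024, ahead of the final analysis, so the benefit in this trial is limited to participants still on treatment when the edit takes effect. The nearly identical parallel study should be checked for the same wording; its text was not available.

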16.2 Appendix 2: Liver event and laboratory trigger definitions & follow-up requirements

Table 16-1 Liver event and laboratory trigger definitions

	Definition/ threshold
Liver laboratory triggers If ALT, AST and total bilirubin normal at baseline:	
 • ALT or AST > 5 × ULN • ALP > 2 × ULN (in the absence of known bone pathology) • Total bilirubin > 3 × ULN (in the absence of known Gilbert syndrome) • ALT or AST > 3 × ULN and INR > 1.5 • Potential Hy's Law cases (defined as ALT or AST > 3 × ULN and Total bilirubin > 2 × ULN [mainly conjugated fraction] without notable increase in ALP to > 2 × ULN) • Any clinical event of jaundice (or equivalent term) • ALT or AST > 3 × ULN accompanied by (general) malaise, fatigue, abdominal pain, nausea, or vomiting, or rash with eosinophilia • Any adverse event potentially indicative of a liver toxicity

ALP: Alkaline phosphatase, ALT: Alanine aminotransferase, AST: Aspartate aminotransferase, ULN: upper limit of normal

Table 16-2 Follow up requirements for liver laboratory triggers ALT, AST, and TBL

Trigger	Liver Symptoms	Action Taken		
		Monitoring	Follow-up Monitoring	Study Medication
ALT				
ALT > 3 ULN TBL normal, or no change for participants with Gilbert's syndrome	None	Measure ALT, AST, ALP, GGT, TBL, INR, albumin, CK, and GLDH in 48-72 hours	Follow up for symptoms	Continue dosing
ALT > 5 x ULN for more than two weeks TBL normal, or no change for participants with Gilbert's syndrome	None	Measure ALT, AST, ALP, GGT, TBL, INR, albumin, CK, and GLDH in 48-72 hours	Follow-up for symptoms Initiate close monitoring and workup for competing etiologies	Interrupt Study drug can be restarted only if another etiology is identified and liver enzymes return to baseline

Trigger	Liver Symptoms	Action Taken		
		Monitoring	Follow-up Monitoring	Study Medication
ALT > 8 x ULN TBL normal, or no change for participants with Gilbert's syndrome	None	Measure ALT, AST, ALP, GGT, TBL, INR, albumin, CK, and GLDH in 48-72 hours	Follow-up for symptoms Initiate close monitoring and workup for competing etiologies	Interrupt Study drug can be restarted only if another etiology is identified and liver enzymes return to baseline
ALT > 3 x ULN TBL > 2 x ULN (or INR > 1.5) For participants with Gilbert's syndrome: Doubling of direct bilirubin	None	Measure ALT, AST, ALP, GGT, TBL, INR, albumin, CK, and GLDH in 48-72 hours	Follow-up for symptoms Initiate close monitoring and workup for competing etiologies	Interrupt Study drug can be restarted only if another etiology is identified and liver enzymes return to baseline
ALT > 3 x ULN TBL normal or elevated	Severe fatigue, nausea, vomiting, right upper quadrant pain	Measure ALT, AST, ALP, GGT, TBL, INR, albumin, CK, and GLDH in 48-72 hours	Follow-up for symptoms Initiate close monitoring and workup for competing etiologies	Interrupt Study drug can be restarted only if another etiology is identified and liver enzymes return to baseline
Total Bilirubin (isolated)				
>1.5 – 3.0 ULN		Repeat LFTs within 48-72 hours	Monitor LFTs weekly until resolution ¹ to ≤ Grade 1 or to baseline	Continue dosing
> 3 - 10 × ULN (in the absence of known Gilbert syndrome)		Repeat LFT within 48-72 hours Hospitalize if clinically appropriate Establish causality Record the AE and contributing factors (e.g., conmeds, med hx, lab) in the appropriate CRF	Monitor LFTs weekly until resolution ¹ to ≤ Grade 1 or to baseline (ALT, AST, total bilirubin, Alb, PT/INR, ALP and GGT) Test for hemolysis (e.g., reticulocytes, haptoglobin, unconjugated [indirect] bilirubin)	Interrupt
> 10 x ULN		Hospitalize the participant Establish causality	ALT, AST, total bilirubin, Alb, PT/INR, ALP and GGT until	Discontinue treatment immediately

		Action Taken		
Trigger	Liver Symptoms	Monitoring	Follow-up Monitoring	Study Medication
		Record the AE and contributing factors (e.g., conmeds, med hx, lab) in the appropriate CRF	resolution ¹ (frequency at investigator discretion)	
General Clinical Symptoms				
Any AE potentially indicative of a liver toxicity including: (General) malaise, fatigue, abdominal pain, nausea, or vomiting, or rash with eosinophilia		Establish causality Record the AE and contributing factors (e.g., conmeds, med hx, lab) in the appropriate CRF	Investigator discretion	Consider study treatment interruption or discontinuation

¹ Resolution is defined as an outcome of one of the following: (1) return to baseline values, (2) stable values at three subsequent monitoring visits at least 2 weeks apart, (3) remain at elevated level after a maximum of 6 months, (4) liver transplantation, and (5) death

[figure not shown]
Alb: Albumin, ALP: Alkaline phosphatase, ALT: Alanine aminotransferase, AST: Aspartate aminotransferase, CK: Creatinine kinase, CRF: Case report form, GGT: Gamma-glutamyl transferase, GLDH: glutamate dehydrogenase, INR: International Normalized Ratio, LFTs: Liver function tests, Med Hx: medical history, PT: Prothrombin time, TBL: Total bilirubin, ULN: upper limit of normal

Table 16-3 Follow up requirements for liver laboratory triggers - Isolated Hyperbilirubinemia

Criteria	Actions required	Follow-up monitoring
Total Bilirubin (isolated)		
>1.5 – 3.0 ULN	- Maintain treatment- Repeat LFTs within 48-72 hours	Monitor LFTs weekly until resolution to ≤ Grade 1 (≤ 1.5 ULN) or to baseline
> 3 - 10 × ULN (in the absence of known Gilbert syndrome)	- Interrupt treatment - Repeat LFT within 48-72 hours - Hospitalize if clinically appropriate - Establish causality - Record the AE and contributing factors (e.g., conmeds, med hx, lab) in the appropriate CRF	- Monitor LFTs weekly until resolution to ≤ Grade 1 (≤ 1.5 ULN) or to baseline (ALT, AST, total bilirubin, Alb, PT/INR, ALP and GGT) - Test for hemolysis (e.g., reticulocytes, haptoglobin, unconjugated [indirect] bilirubin)
> 10 x ULN	- Discontinue the study treatment immediately - Hospitalize the participant - Establish causality	ALT, AST, total bilirubin, Alb, PT/INR, ALP and GGT until resolution (frequency at investigator discretion)

	
- Record the AE and contributing factors (e.g., conmeds, med hx, lab) in the appropriate CRF	
Any AE potentially indicative of a liver toxicity	
- Consider study treatment interruption or discontinuation- Hospitalization if clinically appropriate- Establish causality- Record the AE and contributing factors (e.g., conmeds, med hx, lab) in the appropriate CRF	Investigator discretion

Based on investigator's discretion investigation(s) for contributing factors for the liver event can include: Serology tests, imaging and pathology assessments, hepatologist's consultancy; obtaining more detailed history of symptoms and prior or concurrent diseases, history of concomitant drug use, exclusion of underlying liver disease.

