 - Drug interrupted/permanently discontinued
6. Its outcome (i.e., recovery status or whether it was fatal)

Conditions that were already present at the time of informed consent should be recorded in medical history of the participant.

Adverse events (including lab abnormalities that constitute AEs) should be described using a diagnosis whenever possible, rather than individual underlying signs and symptoms.

Adverse event monitoring should be continued for at least 30 days following the last dose of study treatment.

Once an adverse event is detected, it must be followed until its resolution or until it is judged to be permanent (e.g., continuing at the end of the study), and assessment must be made at each visit (or more frequently, if necessary) of any changes in severity, the suspected relationship to the interventions required to treat it, and the outcome.

Information about adverse drug reactions for the investigational drug can be found in the Investigator's Brochure (IB).

Abnormal laboratory values or test results constitute adverse events only if they fulfill at least one of the following criteria:

- they induce clinical signs or symptoms
- they are considered clinically significant
- they require therapy

Clinically significant abnormal laboratory values or test results must be identified through a review of values outside of normal ranges/clinically notable ranges, significant changes from baseline or the previous visit, or values which are considered to be non-typical in participant with the underlying disease. See [Section 16.1](#) , [Section 16.2](#) and [Section 16.3](#) for alert ranges for laboratory and other test abnormalities.

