10.2 Additional Safety Monitoring

10.2.1 Liver safety monitoring

To ensure participant safety and enhance reliability in determining the hepatotoxic potential of an investigational drug, a standardized process for identification, monitoring and evaluation of liver events has to be followed.

Please refer to [Table 16-1](#) in [Section 16.2](#) for complete definitions of liver laboratory triggers.

Once a participant is exposed to study treatment, every liver event defined in [Table 16-1](#) should be followed up by the investigator or designated personnel at the trial site, as summarized below. Additional details on actions required in case of liver events are outlined in [Table 16-2](#) and [Table 16-3](#). Repeat liver chemistry tests (i.e., ALT, AST, TBL, PT/INR, ALP and GGT) to confirm elevation.

These liver chemistry repeats will be performed using the central laboratory. If results will not be available from the central laboratory, then the repeats can also be performed at a local laboratory to monitor the safety of the participant. If a liver event is subsequently reported, any local liver chemistry tests previously conducted that are associated with this event should have results recorded on the appropriate CRF.

- If the initial elevation is confirmed, close observation of the participant will be initiated, including consideration of treatment interruption if deemed appropriate.
- Discontinuation of the investigational drug (refer to [Section 9.1](#) and [Section 16.2](#)), if appropriate
- Hospitalization of the participant if appropriate
- Causality assessment of the liver event
- Thorough follow-up of the liver event should include, based on investigator's discretion:
 - serology tests, imaging and pathology assessments, hepatologist's consultancy; obtaining more detailed history of symptoms and prior or concurrent diseases, history of concomitant drug use, exclusion of underlying liver disease

All follow-up information and procedures performed must be recorded as appropriate in the CRF.

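### Table 16-1 states its liver triggers only for normal baseline ALT, AST and bilirubin, so some eligible participants lose the automatic follow-up for certain AST rises and for ALP

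*Protocol*

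**What the plan says.** **Triggers.** Protocol section 16.2, Table 16-1, has eight items under the condition "If ALT, AST and total bilirubin normal at baseline". There is no second branch. Section 10.2.1 cites this table as the full definition of the liver laboratory triggers.

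**Follow-up.** Section 10.2.1 attaches the follow-up to that table: "Once a participant is exposed to study treatment, every liver event defined in" Table 16-1 should be followed up. The first step is "Repeat liver chemistry tests (i.e., ALT, AST, TBL, PT/INR, ALP and GGT) to confirm elevation". The next is "If the initial elevation is confirmed, close observation of the participant will be initiated", with treatment interruption to be considered.

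**Eligibility.** Criterion 21 in section 5.2 excludes, on enzymes, only "Aspartate Aminotransferase (AST)/ Alanine Aminotransferase (ALT) levels of more than 1.5 x upper limit of normal (ULN") at screening. It also excludes hepatic disease and INR above 1.5. It sets no limit on bilirubin or ALP.

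**Actions.** Tables 16-2 and 16-3 set out actions by ALT level, bilirubin level and adverse event or symptom. Their rows carry no normal-baseline condition.

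**Analysis.** SAP section 2.7.3, Table 2-16, counts AST and ALP criteria whenever they are newly met after baseline, whether or not baseline values were normal.

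**The concern.** A participant with AST at 1.2 × ULN, or with bilirubin above normal, can be eligible and yet fall outside the Table 16-1 condition. If no other table supplies the missing AST and ALP thresholds, a rise that would prompt confirmatory chemistry in one participant prompts nothing automatic in another. Whether anything happens then depends on the investigator's reading of an out-of-range result.

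At stake is the uniformity of liver safety follow-up, which section 10.2.1 presents as a standardized process. The primary analysis and its inference are not affected.

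**Working it through.** No sample-size or error-rate figure is involved. The check sets the tables side by side and asks which AST or ALP triggers survive for a participant with abnormal baseline ALT, AST or bilirubin.

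**Step 1. Who falls outside the condition.** Anyone with screening AST or ALT above 1.0 and up to 1.5 × ULN that remains abnormal at baseline, anyone with bilirubin above normal, and anyone whose values become abnormal between screening and baseline.

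**Step 2. Which Table 16-1 items use AST or ALP.** Five of the eight: AST > 5 × ULN; ALP > 2 × ULN; AST > 3 × ULN with INR > 1.5; AST > 3 × ULN with bilirubin > 2 × ULN (potential Hy's Law); AST > 3 × ULN with symptoms.

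**Step 3. Whether another table supplies them.** Table 16-2 has 5 ALT rows + 3 bilirubin rows + 1 adverse-event or symptom row = 9 rows. The 4 rows of Table 16-3 repeat rows of Table 16-2, so there are 9 distinct rows. None is entered on an AST or ALP value; both enzymes appear only as tests to repeat or monitor.

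**Step 4. What remains for each of the five items with an abnormal baseline.**

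| Table 16-1 item | What Tables 16-2 and 16-3 still offer | Result |
|---|---|---|
| AST > 5 × ULN | Nothing if ALT ≤ 3 × ULN, bilirubin ≤ 1.5 × ULN and no symptoms | Automatic follow-up lost |
| AST > 3 × ULN with INR > 1.5 | Nothing under the same limits; the INR row needs ALT > 3 × ULN | Automatic follow-up lost |
| ALP > 2 × ULN | No row is entered on ALP | Automatic follow-up lost |
| AST > 3 × ULN with bilirubin > 2 × ULN | Bilirubin rows start above 1.5 × ULN; up to 10 × ULN they ask for repeat liver tests in 48 to 72 hours, then weekly | Uncertain: those rows are headed as isolated bilirubin |
| AST > 3 × ULN with symptoms | The general symptom row names the same symptoms | Causality assessment and CRF recording kept; repeat chemistry not |

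**Step 5. Illustration with assumed values.** Baseline AST 1.2 × ULN; later AST 6 × ULN, ALT 2.8 × ULN, normal bilirubin, no symptoms. AST has risen 6/1.2 = 5-fold. No numeric trigger in the protocol is met. With a normal baseline, the same later values meet the first item of Table 16-1.

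**Step 6. The route through judgement.** Under section 10.1.1 an abnormal result becomes an adverse event if it causes signs or symptoms, requires therapy, or "they are considered clinically significant". Once it is an adverse event suggesting liver toxicity, Tables 16-2 and 16-3 require causality assessment and recording. Further monitoring is left to the investigator, and repeat chemistry is not specified.

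**Step 7. Comparison with the SAP.** Four of the five limbs in Step 2 (all but AST with symptoms) have a matching criterion in SAP Table 2-16, with no normal-baseline condition.

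**Step 8. Whether the existing thresholds suit a mildly raised baseline.** From the AST entry limit of 1.5 × ULN, 5/1.5 = 3.3 and 3/1.5 = 2.0. Crossing the thresholds still needs a rise of more than 3.3-fold or more than 2-fold, so a mild baseline elevation alone would not cross them.

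**The case against.** **These participants remain monitored.** This stands. Someone might infer that an abnormal baseline leaves a participant with no liver triggers, or that all five AST and ALP items are lost. The documents support neither. The ALT rows start at > 3 × ULN with no baseline condition, the bilirubin and symptom rows remain, and section 16.1 has the central laboratory flag every out-of-range value for investigator sign-off. Section 9.1.1 covers discontinuation for laboratory abnormalities, and a DMC reviews safety data.

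**The Hy's Law and symptom limbs are covered elsewhere.** This stands in part. Bilirubin above 2 × ULN arguably enters the bilirubin rows, but their heading leaves that open when AST is also raised. For the symptom limb, entry does not depend on judging the AST rise significant, because the symptoms themselves are listed; only the repeat chemistry is missing.

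**The condition may be a layout artefact.** Jaundice and liver-related adverse events sit beside it and fit poorly under a baseline-enzyme condition. That is a fair doubt. However, the table shows no redaction or gap where a second branch would stand, and no other section supplies one.

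**The follow-up is not strictly mandatory.** Section 10.2.1 says events should be followed up, and several later steps are discretionary. This is correct, so the loss is best described as an automatic prompt.

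**The SAP difference is a contradiction.** A reader might infer this too, and it does not follow. Table 2-16 is a descriptive summary and need not mirror site triggers. It shows only that such cases would be tabulated although the protocol had not prompted confirmation.

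**Conclusion.** The gap is real but narrow. For eligible participants with abnormal baseline ALT, AST or bilirubin, the automatic section 10.2.1 follow-up is clearly lost for three triggers: AST > 5 × ULN and AST > 3 × ULN with INR > 1.5, each within the ALT, bilirubin and symptom limits shown in Step 4, and ALP > 2 × ULN. The Hy's Law limb is unresolved on the text, and the symptom limb loses repeat chemistry only.

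The size in participants cannot be derived, because the documents give no distribution of baseline liver values. Criteria 14 and 21 exclude clinically significant and historical hepatic disease, so the group should consist mainly of mild elevations. The conclusion assumes that the condition governs the Table 16-1 items as printed and that no row was lost when the PDF was read. It merits a cheap correction at the next amendment and is not a reason to question the safety plan as a whole.

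**What to change.** Delete "If ALT, AST and total bilirubin normal at baseline" from Table 16-1, so that its existing thresholds apply to every treated participant. Keep the Gilbert exception on the bilirubin item, and leave criterion 21 and all thresholds as they are. No extra Gilbert rule is needed on the Hy's Law item, which already requires a mainly conjugated fraction.

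The change takes one line in the next amendment and a letter to sites. It adds no scheduled sample: AST and ALP are in the chemistry panel at all 10 scheduled post-baseline visits to Week 52 (Weeks 2, 4, 8, 12, 16, 20, 24, 32, 40 and 52). INR stays at its 5 (Weeks 4, 12, 24, 40 and 52).

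The downside is possibly a few extra liver work-ups, including for ALP, which has no entry limit. The change restores the section 10.2.1 steps only; it does not give AST or ALP a dosing rule in Table 16-2.
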